Cover Page

Statistical Plan

Official Title: The Role of Endogenous Opioidergic Systems in Breathing Based Analgesia

NCT number: NCT03419858

Document Date: August 15, 2016

The Role of Endogenous Opioidergic Systems in Breathing Based Analgesia

Principal Investigator: [name].

Co-Investigators: [name]., [name]., M.P.H.

Sample size determination: We will recruit up to 60 subjects to participate in this study. All subjects (age: 18-55 years) will be pain free, healthy, with no prior meditation experience, and will be recruited from the local community through multiple means. Based on our recent study (Zeidan et al., 2016), a sample size of 18 participants per group will provide 85% power with an alpha level set at 0.05 to detect a partial reversal of pain relief corresponding to a large effect size of $\eta_p^2 = .18$ (g power software 3.0.1). However, to better control for variability in naloxone effectiveness, we will recruit a total of 60 participants (20/group). This sample size was calculated to provide > 90% power to detect a significant difference between groups on VAS pain ratings.

Analyses: In order to test our study hypotheses, we will employ a 3 (group) X 2 (rest vs. manipulation) X 2 (naloxone vs. saline) repeated measures (RM) ANOVA followed by post-hoc paired samples t-tests (in each group) to test the hypotheses that sham-mindfulness meditation and slow-breathing induced analgesia will be reversed by administration of naloxone but not saline. Secondary exploratory analyses will be conducted using the percent change in pain ratings between rest (pre) and manipulation (post) in the presence of naloxone and saline to determine the efficacy of mindfulness meditation-based analgesia as compared to the other two groups. We will also conduct exploratory regression analyses to determine if sham-mindfulness meditation and slow breathing based analgesia are significantly associated with reductions in respiration rate.

References

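### The 85% power stated for detecting a reversal fits a three-group F test; no power is given for the within-group paired t-tests that examine the reversal hypotheses

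*SAP*

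**What the plan says.** The Sample size determination paragraph makes two power statements.

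- For 18 per group: "a sample size of 18 participants per group will provide 85% power with an alpha level set at 0.05 to detect a partial reversal", with the effect size given as a partial eta squared of .18. The basis is the sponsor's recent study and G*Power 3.0.1.
- For 60 participants, 20 per group: "This sample size was calculated to provide > 90% power to detect a significant difference between groups on VAS pain ratings".

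The first names a reversal as its target and the second a difference between groups. For neither does the SAP name a test, degrees of freedom, sidedness or software option.

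The Analyses paragraph plans a repeated measures ANOVA with three groups, rest versus manipulation, and naloxone versus saline. It is followed by "post-hoc paired samples t-tests (in each group) to test the hypotheses that sham-mindfulness meditation and slow-breathing induced analgesia will be reversed" under naloxone but not saline. No power is given for those paired tests.

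**The concern.** Power belongs to a particular test of a particular effect. A test of whether three groups differ in reversal uses everyone enrolled and answers a different question from a paired test of reversal inside one group, which uses a third of them. If all three groups showed the same reversal, however large, the three-group test would reject at only its 5% error rate, while the paired tests could detect it readily.

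The SAP attaches 85% to detecting a reversal, so a reader will take it as the power of the tests that look for one. What is at stake is the reading of a null result. A non-significant paired test in the sham-mindfulness or slow-breathing group could be taken as good evidence against opioid mediation because the trial is described as well powered, although the power of that test was never stated.

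**Working it through.** **Inputs from the SAP:** alpha 0.05; partial eta squared .18; 18 per group (N=54) and 20 per group (N=60); three groups; paired t-tests within each group.

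**Assumptions, not in the SAP:** two-sided t-tests, no dropout, and a paired test that compares pain relief under saline with pain relief under naloxone. The SAP does not define the pairs.

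**Effect size.** f² = .18 / (1 − .18) = .18/.82 = 0.2195, so f = 0.4685.

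**Step 1: reproduce the stated figure.** Three-group F test with 2 and N−3 degrees of freedom and noncentrality λ = N·f².

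| Per group | N | λ | Power | SAP |
|---|---|---|---|---|
| 18 | 54 | 11.85 | 85.8% | 85% |
| 20 | 60 | 13.17 | 89.6% | >90% |

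Eighteen is also the smallest number per group that reaches 85% under this test. The second figure is met only after rounding; 21 per group is the first size above 90% (91.1%). The group by manipulation by drug interaction has this form, because each person contributes one reversal contrast and the test compares its mean across three groups.

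Other tests at the same f² fit less well at 18 per group: two groups only, 78.0%; one degree of freedom on all 54 people, 92.2%; one-group paired test, 46.6%.

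**Step 2: paired t-test if .18 is the within-group reversal.** Then dz = f = 0.4685, λ = n·f², with 1 and n−1 degrees of freedom.

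| n | λ | Two-sided power | With λ = (n−1)·f² | One-sided |
|---|---|---|---|---|
| 18 | 3.95 | 46.6% | 44.5% | 60.4% |
| 20 | 4.39 | 51.2% | 49.2% | 64.6% |

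On this reading 85% power would need 43 per group and 90% would need 50. This is given only to show the size of the gap.

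**Step 3: paired t-test if .18 is a three-group difference in reversal.** Scale the reversal contrast to a within-group SD of 1. Then f² is the variance of the three group means, and the power in any one group depends on how those means are arranged.

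- Reversals (0, d, d): the variance of the means is 2d²/9, so d = √(0.2195 × 9/2) = 0.99. Paired-t power in each reversing group is 97.8% (n=18) and 98.8% (n=20).
- Reversals (0, d/2, d): the variance is d²/6, so d = √(0.2195 × 6) = 1.15 and the middle group has dz = 0.57. Its power is 63.1% (n=18) and 68.3% (n=20).
- Reversals (d, d, d): the variance is 0, so .18 cannot arise and the three-group test has only its 5% error rate.

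These patterns are illustrations; the SAP gives no group means.

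**Step 4: what 20 per group can detect within a group.** Two-sided 0.05, with partial eta squared = dz²/(1 + dz²).

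| Power | dz | Partial eta squared |
|---|---|---|
| 80% | 0.66 | .30 |
| 85% | 0.71 | .33 |
| 90% | 0.76 | .37 |

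**The case against.** The strongest defence has three parts.

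*The test is inferred.* The SAP names none, and the three-group F falls just short of the second figure. A one-group within-subject calculation with two measures and a correlation of .25, using λ = 2n·f²/(1 − .25), gives 86.4% at n=18 and 90.0% at n=20, so numerical fit does not identify the test. This stands as a limit on attribution. It does not supply the missing power: the partial eta squared of a paired contrast already reflects the correlation between the two measures, so applying a correlation again inflates power. The SAP states no correlation either.

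*The ANOVA is itself a planned test.* The Analyses paragraph puts it forward as the test of the study hypotheses, with the paired tests post hoc. Powering an omnibus term and not each follow-up contrast is common, and the second power sentence openly names a group difference. This stands too. A reader might infer that the SAP gives no power for any test it uses; that goes too far. The gap concerns the within-group paired tests, and the labelling of the 85% as power to detect a reversal.

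*The low figure is conditional.* A reader might infer that the trial has roughly half the power it claims. The document does not support that. The 47% and 51% need .18 to be a within-group effect, whereas the test that best reproduces the 85% implies a between-group effect. The two readings cannot be combined. On the between-group reading, equal reversal in the two groups named in the hypotheses gives about 99% at n=20.

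Nor does the title of the cited study settle which contrast .18 came from.

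**Conclusion.** The point holds in a limited form. The 85% can be reproduced, so the sponsor's arithmetic is not shown to be wrong. What is wrong is its label, or else its size. Either it is power for a difference in reversal between groups, described as power to detect a reversal, or, if .18 is the within-group reversal, it exceeds the power of the paired test by about 40 points (85% against 46.6% at n=18).

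In neither case is a stated figure shown to be the power of the paired tests in the sham-mindfulness and slow-breathing groups. That power cannot be determined from the document: about 51% at n=20 on the within-group reading, and 68% or 99% at n=20 for the two between-group patterns worked above. The paired-t figures assume two-sided testing at 0.05, full retention and a saline-versus-naloxone contrast of pain relief.

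**What to change.** Revise the power statements as follows.

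1. Say which effect the partial eta squared of .18 describes: the three-way interaction, another group difference, or the reversal within a group.
2. If it is a group difference, label the 85% (18 per group) and the figure for 20 per group (about 90%, not above it) as power for the between-group or interaction F test, give the assumed pattern of group means, and stop describing either as power to detect a reversal.
3. Define the paired contrast and add its power, for example:

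> With 20 participants in a group, a two-sided 0.05 paired test of saline-minus-naloxone pain relief has 80%, 85% and 90% power for a standardised reversal (dz) of about 0.66, 0.71 and 0.76 (partial eta squared about .30, .33 and .37). If partial eta squared within a group is .18, power is 51%.

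The cost is wording only, with no change to enrolment or to the planned tests. The stated power will look less favourable if .18 proves to be a within-group effect.

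### Does the stated power of more than 90% fail because its ANOVA term is unnamed, its target is worded two ways and it needs all 60 participants?

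*SAP*

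**What the plan says.** Under Sample size determination, the SAP bases its calculation on an earlier study by the same group and states that "a sample size of 18 participants per group will provide 85% power with an alpha level set at 0.05". The target there is "to detect a partial reversal of pain relief corresponding to a large effect size of $\eta_p^2 = .18".

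It then enlarges the groups, giving variability in the effectiveness of naloxone as the reason: "we will recruit a total of 60 participants (20/group"). The closing power statement is "This sample size was calculated to provide > 90% power to detect a significant difference between groups on VAS pain ratings". The section opens with a ceiling on recruitment: "We will recruit up to 60 subjects to participate in this study".

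Under Analyses, the model is a repeated measures ANOVA with factors group (3), rest versus manipulation (2) and naloxone versus saline (2), "followed by post-hoc paired samples t-tests (in each group) to test the hypotheses" that naloxone reverses the analgesia of sham meditation and of slow breathing.

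**The concern.** Four things catch the eye.

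- **Unnamed term.** A three-factor ANOVA has seven effects (three main effects, three two-way interactions and one three-way). The SAP ties .18 to none of them, and the power implied by .18 depends on which test it belongs to.
- **Two targets.** Reversal of pain relief involves the drug factor. A difference between groups on VAS ratings, read literally, need not.
- **The figure itself.** On the reading that best returns the SAP's 85%, power at 60 participants is 89.6%, just short of the claim. Sixty is also the recruitment ceiling, so any loss of participants lowers it further.
- **Follow-up tests.** The paired t-tests within each group carry the reversal hypotheses, yet no power is stated for them.

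If these points held, a reader could not tell what the trial is powered for, and might read a negative result on reversal as better supported than it is.

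**Working it through.** **Inputs from the SAP:** alpha 0.05; partial eta squared .18; 18 per group (N = 54) with 85% power; 20 per group (N = 60) with more than 90%; three groups.

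**Assumed reading:** each person contributes one contrast score, namely pain relief (rest to manipulation) under saline minus that under naloxone. The three groups are compared on it. This is the group by phase by drug interaction, with 2 and N − 3 degrees of freedom.

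**Formula:** f² = η²/(1 − η²) and λ = f² × N. Power is the probability that a noncentral F with parameters (2, N − 3, λ) exceeds the 5% critical value of the central F.

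**The SAP's own figure first.** f² = .18/.82 = 0.2195.

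- N = 54: λ = 0.2195 × 54 = 11.85; critical F(2, 51) = 3.18; power 85.8%. The smallest N to reach 85% is 53 (85.1%), which rounds up to 18 per group. The stated 85% is reproduced.
- N = 60: λ = 0.2195 × 60 = 13.17; critical F(2, 57) = 3.16; power 89.6%. The gap to 90% is 0.4 points.

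**Rounding of the effect size.** A printed .18 stands for any value from .175 to .185.

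| η² | N = 54 | N = 57 | N = 60 |
|---|---|---|---|
| .175 | 84.6% | 86.7% | 88.5% |
| .18 | 85.8% | 87.8% | 89.6% |
| .182 | 86.3% | 88.3% | 90.0% |
| .185 | 87.0% | 88.9% | 90.6% |

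At N = 60 the claim is met from about .182 upwards.

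**Other readings of .18, at 18 and then 20 per group:**

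- one-degree-of-freedom within-person effect: 92.2% and 94.6%
- contrast of two groups: 78.0% and 82.3%
- paired test in a single group: 46.6% and 51.2%
- default repeated-measures settings of the power software: 94% to 100%

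None of these returns 85% at 18 per group. A variant of the 2-degree-of-freedom test with λ = f² × (N − 3) gives 83.7% and 87.9%. It is close, but falls short of the SAP's figure at both sizes.

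**The two wordings.** The hypotheses expect reversal under sham meditation and slow breathing. With no reversal under mindfulness, the interaction is exactly a difference between groups in how far naloxone reverses pain relief. One test can therefore carry both descriptions.

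**Follow-up tests.** Suppose two groups reverse by an equal standardised amount d and the third by none. The variance of the three group means is then (2/9)d². Setting this equal to f² gives d = √(0.2195 × 9/2) = 0.994. A two-sided paired comparison of naloxone with saline then has 98.8% power at n = 20 and 97.8% at n = 18.

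**The case for a change.** The strongest case for acting is that a power figure cannot be interpreted without its test. With .18 applied to different tests, power at 20 per group runs from 51.2% to 94.6% even before the software's default settings are considered. The SAP leaves the reader to infer which test is meant, and naming it would cost a line. There is also no slack: at 19 per group, power is below 90% for every effect size that prints as .18 (86.7% to 88.9%), and the document gives no allowance for participants who lack one drug condition.

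Part of this stands. The term is unnamed, the wording is loose, and the 2-degree-of-freedom reading is an inference. The rest does not carry far.

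- The 51.2% comes from a reading that yields 46.6% where the SAP states 85%, so it is not evidence about what was planned.
- The sentence claiming more than 90% gives no effect size of its own. If its target is a different one, 89.6% does not test it. If it is the same one, the complaint of two targets largely falls away.
- The attrition shortfalls (about 1 to 3 points with one person per group lost, 3 to 5 with two) need a loss that the SAP does not state. Dropout and replacement are commonly left to the protocol, which is not at hand. Losing two per group returns the trial to 18 per group, for which the SAP already states 85%.
- A SAP need not give power for follow-up tests.

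**Conclusion.** No wrong power figure is shown and no change follows. The gap at exactly .18 is 0.4 percentage points, inside the range of 88.5% to 90.6% that the rounding of the effect size allows. What remains is missing detail that a statistician would fill the same way: the group by phase by drug interaction is the natural term, it reproduces the 85%, and it fits both descriptions of the target. Writing it down would leave the 60 participants, the ANOVA, the paired tests and any conclusion as they are.

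This rests on three assumptions: that .18 belongs to that interaction, that it also underlies the sentence claiming more than 90%, and that power is quoted, as is usual, for the planned number. The figure of about 99% for the follow-up tests further assumes equal reversal in two groups and none in the third. It shows only that the plan gives no sign of inadequate power there.
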